#### 9.4.2 ANALYSIS OF THE PRIMARY ENDPOINT

The safety of MKit and the willingness of participants to use it will be assessed through post-intervention semi-structured interviews, conducted with 25 participants including 15 participants from the intervention group and 10 participants from the control group. The usability for the WebApp will be assessed at two time points (1-month and 5-months) using the 10-item System Usability Scale (Brooke, 1996). The acceptability of the WebApp will be assessed at two time points (1-month and 5-months) using an investigator created 5-item acceptability scale. Usability and acceptability scores will be assessed among those in the intervention group.

For the semi-structured interviews, all audiotapes will be transcribed verbatim. Data analyses will be conducted using an iterative process and the constant comparative method of analysis (Glaser, 1992). Member checking will contribute to credibility through validation of the research findings by participants. A codebook will be developed after repeated high-level reading of the

transcripts by the study team. Data will be coded and grouped into categories to facilitate abstraction and concept analysis. An audit trail will be established to allow others to follow the decisions made by the research team (Sandelowski & Barroso, 2003). The results of the semi-structured interviews will be used to: 1) update the content of MKit, as needed; 2) assess the safety of MKit; 3) assess the usability and willingness to use MKit; and 4) assess the acceptability of MKit.

---

#### 9.4.3 ANALYSIS OF THE SECONDARY ENDPOINT

Preliminary analyses of the survey data (knowledge, attitudes, and experiences related to sexual and intimate partner violence) will be analyzed using the Statistical Package for the Social Sciences (SPSS); all p-values will be set at  $<.05$ . Descriptive statistics will be assessed first. The baseline, 1-month post, and 5-month post-intervention tests will be examined for measures of central tendency, measures of dispersion, and frequency distribution on outcomes. Analysis of variance (ANOVA) will be utilized to determine if the scores on the baseline and follow-up tests differ significantly among the two arms. Usability and acceptability scores will be assessed among those in the intervention group.

We are not powered to assess outcome measures; however, we will look at the direction of effects for our outcome measures to allow for power calculations for future scale-up.

---

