## 1.2 SCHEMA

## 1.3 SCHEDULE OF ACTIVITIES (SOA)

Procedures	Preparation before recruitment	Baseline	1-month follow-up	5-month follow-up	Post-study semi-structured interviews
Randomization by residence hall	X				
Demographics		X	X	X	
Sexual and Intimate Partner Violence Knowledge		X	X	X	
Self-Efficacy of Protective Behaviors Related to Sexual and Intimate Partner Violence		X	X	X	
Intimate Partner Violence Attitude Scale		X	X	X	
Consensual Sexual Activity		X	X	X	
Sexual Experiences Survey (Victimization and Perpetration)		X	X	X	
Universal Violence Prevention Screening		X	X	X	
System Usability Scale			X	X	
System Acceptability			X	X	
User Data			X	X	
Reaction to content					X
Perceived safety					X
Desirability					X
Willingness for future use					X

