
Secondary
 
To complete preliminary evaluations on retention and efficacy measures, such as sexual and intimate partner violence knowledge, attitudes, and experiences (victimization and perpetration) to allow for power calculations for a future R-level submission.
	
Retention will be measured as the percentage of participants completing the 1- and 5-month follow-up surveys.
 
Sexual and Intimate Partner Violence Knowledge will be measured with 20 items adapted from the Texas Education Program Participant Response Form (https://www.wcasa.org/file_open.php?id=787).
 
Confidence in the ability to handle situations related to sexual and intimate partner violence will be measured using 15 investigator created items that called the, Self-Efficacy of Protective Behaviors Related to Sexual and Intimate Partner Violence.
 
Attitudes related to Intimate Partner Violence Attitude Scale will be measured using 34 items adapted from Finchman, Cuit, Braithwaite, & Pasley (2008).
 
Consensual Sexual Activity will be measured with 2 primary questions developed by the investigators.
 
Sexual victimization (n=10) and perpetration (n=10) will be measured with the Sexual Experiences Survey (Koss et al., 2007).
 
Experiences of intimate partner violence will be measured with 26 items adapted from the Universal Violence Prevention Screening (Heron, Thompson, Jackson, & Kaslow, 2003).
	
The endpoints are important, as the WebApp under study is a primary sexual violence prevention intervention with a focus on healthy relationships. As such, knowledge, attitudes, and experiences of sexual and intimate partner violence victimization and perpetration are outcomes of interest. Though this pilot study is not powered to detect changes in these secondary outcomes, obtaining data for power calculations for a larger study is a key component of this study.

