## 4 STUDY DESIGN

### 4.1 OVERALL DESIGN

This project builds on the current momentum to address the primary prevention of sexual violence within United States institutions of higher education as well as the proliferation of web-based applications. A before-and-after quasi-experimental, mixed-method pilot design will be used to gather acceptability and safety data as well efficacy trends. Two residence halls (Alice Lloyd and Couzens) at the University of Michigan will be randomized to receive either: (1) the control arm (n=150) which will receive usual care only (all incoming students receive three programs about healthy relationships and sexual violence including Haven, Relationship Remix, and Change it Up) or (2) the usual care (n=150) described above and the web-based intervention (MKit). We will use cluster-randomization by residence hall (to minimize contamination associated with individual-level randomization of students living in the same residence hall). Following the informed consent process, students in both conditions will complete a baseline survey of xx questions. Baseline measures will include: 1) demographic data (n=12), 2) investigator developed questions on knowledge about sexual and intimate partner violence (n=20) adapted from the Texas Education Program Participant Response Form ([https://www.wcasa.org/file\\_open.php?id=787](https://www.wcasa.org/file_open.php?id=787)), 3) investigator developed questions on self-efficacy (n=15), 4) 34 questions from the Revised Intimate Partner Violence Attitude Scale (Finchman, Cuit, Braithwaite, & Pasley, 2008), 5) investigator developed questions on consensual sex (n=2), 6) 10 items from the Sexual Experiences Survey (SES) will measure past experiences with sexual violence (Koss et al., 2007) and 10 items from the Sexual Experiences Survey (SES) will measure past experiences with perpetration (Koss et al., 2007), and 7) 26 questions from the Universal Violence Prevention Screening Protocol – Adapted questions (Heron, Thompson, Jackson, & Kaslow, 2003). All of these are measures have been validated and used extensively in the United States to measure knowledge and attitudes related to gender-based violence. Following the survey, students in the Intervention group will be given the opportunity to interact with the application at their own pace, choosing which content to view in the order they prefer.

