The Control group will only receive the usual care delivered to all incoming University of Michigan students, which includes Haven (an online course about sexual violence), Relationship Remix (an interactive program about healthy relationships and sexual violence delivered by peers), and Change it Up (a theater based performance on bystander intervention). The Intervention group will receive the usual care described above as well as access to MKit. They will be encouraged to interact with MKit throughout the study. Data will be collected on the content viewed by the participants, as well as the amount of time they spend within each content area, and the order in which they view the content.

At 1 and 5 months, we will repeat all baseline measures in both groups. Participants in the Intervention group will also be asked to complete the 10-item System Usability Scale (Brooke, 1996) and an investigator created 5-item acceptability scale.

Post-intervention semi-structured interviews will be conducted with 25 participants, including 15 participants from the intervention group and 10 participants from the control group, to assess perceived safety, reaction to content, desirability, willingness to continue using the content, and willingness to recommend the content to others. Prior to commencing the interviews, we will ask each participant to complete a paper demographic survey.

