### 5.5 STRATEGIES FOR RECRUITMENT AND RETENTION

Students from the target sample, first-year University of Michigan college students, will be recruited for the study. Two residence halls (Alice Lloyd and Couzens) at the University of Michigan will be randomized to receive either: (1) the control arm ( $n=150$ ) which will receive usual care only (all incoming students receive three programs about healthy relationships and sexual violence including Haven, Relationship Remix, and Change it Up) or (2) the usual care ( $n=150$ ) described above and the web-based intervention (MKit). We will use cluster-randomization by residence hall (to minimize contamination associated with individual-level randomization of students living in the same residence hall). At the end of the Relationship

Remix program, a brief announcement will be made about the opportunity to participate in a research study about healthy relationships and palm cards will be distributed (see recruitment materials). We will recruit specifically from Relationship Remix to ensure that all experimental and control subjects receive the same primary prevention programming currently in place on campus. Interested students will receive a palm card with a link to either the MKit web-based application (Intervention) with an access code to sign-up for the website, or a link to the baseline consent and Qualtrics survey (Control) without access to the web-based application. At the end of the study, students from each condition will be invited to participate in an in-person semi-structured interview. Students will receive the invitation to participate in the semi-structured interview on the final page of their 5-month follow-up survey. Students who opt to share their email address with the study team at that time will be contacted to set-up an in-person interview based on user status for the intervention (consistent user of MKit, frequent user of MKit, minimal user of MKit) and a diverse group based on gender, race/ethnicity, and age for the control group. Semi-structured interviews will be conducted with participants from both the Control group (n=10) and the Intervention group (n=15).

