### 9.4 STATISTICAL ANALYSES

#### 9.4.1 GENERAL APPROACH

The survey data will be analyzed using the Statistical Package for the Social Sciences (SPSS); all p-values will be set at  $<.05$ . Descriptive statistics will be assessed first. The baseline, 1-month post, and 5-month post-intervention tests will be examined for measures of central tendency, measures of dispersion, and frequency distribution on outcomes. Analysis of variance (ANOVA) will be utilized to determine if the scores on the baseline and follow-up tests differ significantly among the two arms. Usability and acceptability scores will be assessed among those in the intervention group.

We are not powered to assess outcome measures (sexual violence experiences/behaviors, rape myth acceptance, or sexual relationship power); however, we will look at the direction of effects for our outcome measures to allow for power calculations for a future R-Level submission. The results of this project will establish the safety and usability of this adapted web-based application for future scale-up.

For the semi-structured interviews, all audiotapes will be transcribed verbatim. Data analyses will be conducted using an iterative process and the constant comparative method of analysis (Glaser, 1992). Member checking will contribute to credibility through validation of the research findings by participants. A codebook will be developed after repeated high-level reading of the transcripts by the study team. Data will be coded and grouped into categories to facilitate abstraction and concept analysis.

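### The ANOVA planned for the secondary survey scores names no change-from-baseline contrast, so with one residence hall per arm a stable gap between halls can pass in full into the effect estimate

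*Combined protocol and SAP*

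**What the plan says.** Section 4.1 describes the design in these words: "A before-and-after quasi-experimental, mixed-method pilot design will be used to gather acceptability and safety data as well efficacy trends". Two residence halls are randomized, one to each arm, with 150 students planned in each. The schedule in section 1.3 places "Randomization by residence hall" in the preparation stage, before recruitment. Under section 5.5 the invitation differs by arm: "Interested students will receive a palm card with a link to either the MKit web-based application (Intervention) with an access code", while control students receive a link to the consent form and survey only. Section 6.3 states that there is no blinding.

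The survey measures are taken in both arms three times: "At 1 and 5 months, we will repeat all baseline measures in both groups". The analysis in section 9.4.3, repeated word for word in 9.4.1, is descriptive statistics followed by "Analysis of variance (ANOVA) will be utilized to determine if the scores on the baseline and follow-up tests differ significantly among the two arms", with a significance level of .05. Section 9.4.5 compares demographic characteristics at baseline but specifies no adjustment.

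On the use of the results, section 3 says that "obtaining data for power calculations for a larger study is a key component of this study", and section 9.4.1 adds: "we will look at the direction of effects for our outcome measures to allow for power calculations for a future R-Level submission".

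**The concern.** The ANOVA sentence asks whether scores differ between arms. It does not ask whether they change differently. Two readings fit the words:

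- **A separate between-arm test at each survey.** The follow-up test ignores each student's own baseline, so any stable gap between the halls appears whole in the follow-up difference.
- **A repeated-measures ANOVA read through its main effect of arm.** This also carries the whole gap. It also shrinks a constant true effect to two-thirds, because the baseline survey is averaged in.

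Only the arm-by-time contrast cancels a stable gap, and it is not named. A gap is plausible here: there is one hall per arm, halls are allocated before students are approached, and students volunteer knowing what their arm offers.

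At stake are the sign and size of the effects handed to the next trial's power calculation. The primary endpoints and retention are not affected.

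**Working it through.** The plan states no power, effect size or sample-size figure for these outcomes (section 9.2 says no formal calculation was done), so there is nothing to reproduce.

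**Inputs from the documents:** n = 150 per arm, one hall per arm, three surveys, test level 0.05 (taken as two-sided).

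**Assumed, because the documents give no values:** SD 1; stable gap g = 0.10 to 0.30 SD; equal correlation r = 0.3 to 0.7 between surveys; no attrition; student-level error only.

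**Expected estimate** with true effect d (constant at both follow-ups) and stable gap g:
- separate follow-up test: d + g
- main effect of arm over three surveys: 2d/3 + g
- baseline-adjusted (ANCOVA): d + g(1 − r)
- change from baseline: d

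So the sign reverses only if the gap opposes the effect and exceeds it (separate tests) or exceeds two-thirds of it (main effect). Example with d = 0.20 and g = −0.15: separate 0.05; main effect 0.133 − 0.15 = −0.017; ANCOVA 0.095 to 0.155; change 0.20.

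**Standard errors.** The base is √(2/150) = 0.1155. Multiply by √((1+2r)/3) for the main effect, √(1−r²) for ANCOVA and √(2(1−r)) for change.

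**Rejection rate with no true effect** = Φ(b/SE − 1.96) + Φ(−b/SE − 1.96), where b is the part of the gap that remains. For g = 0.20:

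| Analysis | Gap remaining (SD), r = 0.3 / 0.5 / 0.7 | SE | Rejection |
|---|---|---|---|
| Separate test | 0.20 at any r | 0.1155 at any r | 41% |
| Main effect of arm | 0.20 at any r | 0.084 / 0.094 / 0.103 | 66 / 56 / 49% |
| ANCOVA | 0.14 / 0.10 / 0.06 | 0.110 / 0.100 / 0.082 | 25 / 17 / 11% |
| Change from baseline | 0 | 0.137 / 0.115 / 0.089 | 5% |

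For g = 0.10 and 0.30 the separate test rejects 14% and 74%. A simulation at r = 0.5 and g = 0.20 (4,000 runs) gave 42% for the separate 5-month test (mean estimate 0.200), 57% for the main effect and 4.8% for change (mean −0.0004). With 105 students per arm, the separate-test figure at g = 0.20 falls from 41% to about 30%.

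**Gap treated as random.** With a hall ICC of 0.01 the difference between halls has SD √(2 × 0.01) = 0.14. The rate 2(1 − Φ(1.96·SE/√(0.02 + SE²))) is then 22% for separate tests and 32 to 25% for the main effect. It stays at 5% for change if the gap is stable.

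**Planning consequence.** Size per arm for 80% power, before any design effect, is 2(1.96 + 0.8416)²/d² = 15.70/d². A true effect of 0.20 needs 393. A 0.10 SD gap moves the separate-test estimate to 0.10 or 0.30, giving 1,570 or 175.

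**Limit of the change contrast.** If a hall effect with ICC 0.01 arises after baseline, the true SE is √(2(0.01 + 0.99·2(1−r)/150)) = 0.196 / 0.182 / 0.167. The student-level values on the same basis are 0.136 / 0.115 / 0.089, so the interval is 1.4 to 1.9 times too narrow.

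**The case against.** **The text may be loose rather than wrong.** A repeated-measures ANOVA with an interaction may have been intended, given the before-and-after label and the three surveys. That is possible, and the bias figures would then not apply. But the contrast is not named, and two analysts could follow the sentence and report different effects.

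**A gap would be visible.** Baseline scores are to be tested between arms and described at every survey. This makes an unnoticed carry-over less likely, but seeing a gap does not remove it from the follow-up estimate or its p-value.

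**The gap size has no anchor, and both arms are recruited at the same campus programme.** Both points stand. The 0.20 SD figure is an illustration, and the random-gap version gives about half the rejection rate. That a stable gap passes through whole is algebra and does not depend on its size.

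**Sampling error alone is as large.** One standard error around 0.20 spans 0.0845 to 0.3155, or about 2,200 to 158 per arm, which is wider than the gap-induced range. True, and the change contrast does not reduce this noise when r is 0.5 or lower. But a confidence interval shows sampling error; it does not show a bias.

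**Change can over-correct.** If the baseline difference is partly transient, subtracting it introduces error the other way. This is a good reason to report ANCOVA alongside.

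**Linkage.** Section 10.1.3 bars linking identifying information to survey data and describes no survey code. Yet section 4.4 (completion of all three surveys) and sections 7.1 to 7.3 (attrition analyses) already presuppose tracking within student. The plan should say how this is done.

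**Conclusion.** The concern holds. As written, the plan for the secondary survey scores does not use each student's baseline, and under either reading above a stable gap between the two halls enters the estimate in full. Under the stated assumptions, a 0.20 SD gap turns a nominal 5% test into one that rejects 41% of the time (separate tests) or 49 to 66% (main effect of arm). A 0.10 SD gap shifts the later trial's size by a factor of about 2 to 4.

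The gap, correlation and ICC are assumptions, and an interaction may have been meant. The outcomes are secondary and unpowered, so this is a worthwhile correction and not a threat to the primary objective. It bears directly on the secondary aim of supplying planning figures.

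**What to change.** In sections 9.4.1 and 9.4.3, replace the ANOVA sentence for the scale scores with the following:

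- A linear mixed model (SPSS MIXED) of the baseline, 1-month and 5-month scores, with arm, time and arm-by-time terms, unstructured covariance within student, arms not constrained equal at baseline, and all available surveys used.
- The effect defined as the between-arm difference in change from baseline at 1 month and at 5 months, with 95% intervals.
- The ANCOVA difference as a sensitivity analysis, noting that it leaves (1 − r) of a stable gap, whereas change over-corrects a transient one.
- The SD and the baseline-to-follow-up correlation reported for planning.
- For the experience items, the analogous arm-by-time contrast in a binary or count model, provided the recall window is the same at each survey.
- A statement that the intervals omit hall-level variation, and that with one hall per arm no analysis separates the intervention from hall effects arising after baseline.
- A sentence on how a student's surveys are linked over time without identifying information.

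The cost is wording and slightly more analysis in the same software, with no new measures or visits, provided a linking code exists. Change from baseline is less precise than baseline adjustment, and less precise than the unadjusted comparison when the correlation is below 0.5.

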#### 9.4.4 SAFETY ANALYSES

The safety of MKit will be assessed through post-intervention semi-structured interviews, conducted with 25 participants including 15 participants from the intervention group and 10 participants from the control group.

---

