**Endpoints:**

- Primary: Safety (qualitative interviews), Usability (System Usability Scale, Brooke, 1986), Acceptability (investigator generated), and willingness to use (qualitative interviews).
- Secondary: Retention (percent completing follow-up surveys), Sexual and Intimate Partner Violence Knowledge (adapted from Texas Education Program Participant Response Form), Self-Efficacy of Protective Behaviors Related to Sexual and Intimate Partner Violence (investigator generated), Intimate Partner Violence Attitude Scale (adapted from Finchman, Cuit, Braithwaite, & Pasley, 2008), Consensual Sexual Activity (investigator generated), Sexual victimization/perpetration (Sexual Experiences Survey, Koss et al., 2007), and Universal Violence Prevention Screening (adapted from Heron, Thompson, Jackson, & Kaslow, 2003).

**Study Population:** 300 first year university students (150 Control Group, 150 Intervention Group)

[figure not shown]
**Phase:** Pilot

**Description of  
Sites/Facilities  
Enrolling  
Participants:**

University of Michigan Residence Halls (Alice Lloyd and Couzens)

Description of Study Intervention:	Web-based app that uses a life skills approach to address healthy relationships and sexual violence.
Study Duration:	2 years 9 months
Participant Duration:	For pilot study – 6 months

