## 3 OBJECTIVES AND ENDPOINTS

Objectives	Endpoints	Justification for Endpoints
Primary		
To evaluate the safety, usability, acceptability, and willingness of using the adapted WebApp among a randomized sample	Safety will be assessed through qualitative interviews  Usability will be measured through the System Usability Scale (Brooke, 1986)	The endpoints are common outcomes of interest for studies of technological interventions. These outcomes will be measured throughout

of 300 first year university students.	
Acceptability will be measured through an investigator generated scale
 
Willingness to use will be assessed through qualitative interviews
	
the study, to observe changes overtime with continued exposure to the intervention. These endpoints are important outcomes, as interventions must be safe, acceptable, and usable to ensure broad scale uptake.

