#### 4.2 SCIENTIFIC RATIONALE FOR STUDY DESIGN

This is a before-and-after quasi-experimental, mixed-method pilot design with three survey collection points and a post-study semi-structured interview component. This study will be performed with healthy college students to determine the safety, acceptability, and usability of MKit.

The endpoints are common outcomes of interest for studies of technological interventions. These outcomes will be measured throughout the study, to observe changes over time with continued exposure to the intervention. These endpoints are important outcomes, as interventions must be safe, acceptable, and usable to ensure broad scale uptake. MKit is a primary sexual violence prevention intervention focused on healthy relationships. As such, knowledge, attitudes, and experiences of sexual and intimate partner violence victimization and perpetration are outcomes of interest. Though this pilot study is not powered to detect changes in these secondary outcomes, obtaining data for power calculations for a larger study is a key component of this study.

This study compares usual care for the prevention of sexual and intimate partner violence with care as usual plus the intervention. Both groups will receive interventions currently in place, ensuring that standard care is not withheld from any participant. As the intervention under study is intended to supplement and reinforce current primary prevention programming, the study design will measure the acceptability and preliminary efficacy of broad scale-up of the intervention to the broader college campus.

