## 8.2 SAFETY AND OTHER ASSESSMENTS

The safety of MKit will be assessed through post-intervention semi-structured interviews, conducted with 25 participants including 15 participants from the intervention group and 10 participants from the control group.

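### Safety and willingness to use, two of the four primary endpoints, are analysed only from 25 end-of-study interviews (15 with MKit access), and recorded adverse events are left out of section 9; this can explore perceived safety but not establish it

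*Combined protocol and SAP*

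**What the plan says.** The primary objective has four parts: safety, usability, acceptability and willingness to use. Section 3 assigns the first to interviews: "Safety will be assessed through qualitative interviews". It assigns willingness to the same source, as does the Synopsis. Section 8.2 repeats this for safety ("The safety of MKit will be assessed through post-intervention semi-structured interviews"), and section 9.3 draws both endpoints from the interview participants. Section 9.4.4 adds only that the interviews are "conducted with 25 participants including 15 participants from the intervention group and 10 participants from the control group".

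On timing, section 4.2 says of the endpoints: "These outcomes will be measured throughout the study, to observe changes over time with continued exposure to the intervention". Section 3 says the same in the row for the primary objective. In the schedule of activities (1.3), "Perceived safety" and "Willingness for future use" are marked only in the post-study interview column.

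On selection, section 5.5 puts the interview invitation on the final page of the 5-month survey, and students choose whether to give an email address. Intervention interviewees are then chosen by level of MKit use. Control students have no access to MKit.

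On adverse events, section 8.3.4 requires them to be recorded from consent to the last day of participation. Nothing in sections 9.1 to 9.4.9 mentions them. Section 9.4.8 lists individual data by measure and time point, which is not an adverse-event summary.

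On the conclusion, section 9.4.1 states that the results will establish the app's safety and usability for scale-up. Section 9.1 and the Synopsis hypothesise that the app is safe, with no criterion for judging it.

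**The concern.** The intended safety conclusion is stronger than the data assigned to it. Followed as written, section 9 produces a statement about safety from volunteers who completed follow-up. It has no denominator, and the adverse events that the protocol itself requires to be recorded do not enter it. Students who left the study before month 5 are outside this analysis, and they are the group in which distress would matter most. Ten of the 25 interviewees never had the app, and the text does not say what their interviews contribute to a finding about it.

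The stake is the scale-up decision. A larger study could cite this pilot as having shown safety when it had explored perceived safety in a small, self-selected group.

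**Working it through.** **Sources set side by side**

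| Question | Where the plan answers | Answer |
|---|---|---|
| Source of safety and willingness data | Synopsis; sections 3, 8.2, 9.3, 9.4.2, 9.4.4 | Interviews only |
| When measured | Sections 3 and 4.2 | Throughout the study |
| When measured | Section 1.3 | Once, post-study |
| Who can be interviewed | Section 5.5 | Opt-in volunteers at the end of the 5-month survey |
| Are adverse events recorded? | Section 8.3.4 | Yes, from consent onward |
| How are they detected? | Sections 8.3.4 and 10.1.8 | Passively, at contacts or by email; no row in the schedule |
| Are they analysed? | Section 9 | Not mentioned |

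The two answers on timing conflict. So do the requirement to record adverse events and a safety analysis that does not use them.

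**Numbers.** The plan gives no precision figure for safety or willingness, so there is none to reproduce. Section 9.2 says no formal sample size calculation was done.

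- Interview count: 15 + 10 = 25, which agrees with the text.
- Share interviewed: 15/150 = 10.0% of the intervention arm; 10/150 = 6.7% of controls; 25/300 = 8.3% overall.

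**Illustration of what 15 exposed people can show.** The planned analysis is qualitative coding, so this is a yardstick and not a criticism of that method. It assumes random sampling and a harm that can be counted.

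- Exact two-sided 95% upper limit with no events in n: 1 − 0.025^(1/n).
- n = 15: 1 − 0.025^(1/15) = 0.218, or 21.8%.
- Chance that 15 people include at least one case at true rate p: 1 − (1 − p)^15. For assumed rates of 1%, 2%, 5% and 10% this is 14.0%, 26.1%, 53.7% and 79.4%.
- Willingness: if all 15 were willing, the two-sided 95% lower limit would be 0.025^(1/15) = 0.782, or 78.2%.

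**The same limit if items were put on the intervention-arm surveys.** The documents give no expected response rate, so 50%, 70% and 100% of 150 are assumptions.

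| Assumed response | n | Upper limit with no events |
|---|---|---|
| 50% | 75 | 4.8% |
| 70% | 105 | 3.5% |
| 100% | 150 | 2.4% |

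**The case against.** The best defence is that this is a pilot which section 2.3.1 describes as no more than minimal risk, and that a small purposive interview sample is a legitimate way to explore perceived safety. That stands. The fault lies in the claim and in the missing summary of recorded events, not in the use of interviews. Because the sample is purposive, the binomial limits are only illustrative.

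A reader might infer several stronger points that the documents do not support:

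- *Safety is not monitored.* Section 8.3 requires adverse events to be graded for severity and relatedness and reported immediately to the sponsor. Section 8.4.2 sends unanticipated problems to the IRB within 7 or 14 days. What is missing is their analysis.
- *Students who leave, or who dislike the app, cannot be heard.* Those who leave the study cannot be interviewed, but their adverse events or complaints may still arrive under sections 8.3.4, 8.3.5 and 10.1.8. A student who stops using MKit but stays in the study can be interviewed, and section 5.5 deliberately includes minimal users.
- *Control interviews will be counted as evidence about MKit.* The text is silent. The interview guide is not in the text and may give their purpose.
- *Usability and acceptability are undermined too.* Their survey scores come from the intervention arm only and are unaffected.

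It can also be said that victimisation and partner violence are surveyed in both arms and could serve as harm indicators. Section 8.1 treats them as efficacy measures, however, and sections 9.3 and 9.4.4 do not assign them to safety. The acceptability items are not reproduced, so whether they touch on discomfort or willingness is unknown.

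Finally, the timing sentence may have been meant only for usability and acceptability. The text makes no such exception, but narrowing it is an acceptable remedy.

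**Conclusion.** The point holds in this form. The planned safety and willingness analyses use 25 opt-in, end-of-study interviews, 15 of them with people who had the app. They leave out the adverse events recorded under section 8.3, and their timing contradicts sections 3 and 4.2. This supports an exploratory description of perceived safety and willingness. It does not support a conclusion that safety has been established.

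The 21.8% limit rests on the random-sampling and countable-harm assumptions, and opt-in selection makes the real position less certain than the figure suggests. It is not an estimate of harm, and nothing in the documents suggests that MKit is unsafe. The absence of an adverse-event analysis, the timing conflict and the overstatement are plain from the text. The part about control interviews is less certain, because the interview guide has not been seen. The plan should be corrected, but no survey-based usability or acceptability result is invalidated.

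**What to change.** 1. **Reword the claim** in the Synopsis (Study Description), 9.1 and 9.4.1. For example: the results will describe the usability and acceptability of the application, explore its perceived safety and participants' willingness to use it, and summarise recorded adverse events.
2. **Add a descriptive table to 9.4.4**, by arm and in all enrolled participants, of the adverse events, serious adverse events and unanticipated problems recorded under 8.3 and 8.4. State that detection is passive and unequal between arms (15 versus 10 interviews, and only MKit users can report MKit problems), so the table is not a comparison.
3. **Separate the interviews** in 9.3, 9.4.2 and 9.4.4. Base findings about MKit on the 15 intervention participants. Report the 10 control interviews separately and state their purpose.
4. **Reconcile sections 3 and 4.2 with the schedule.** Preferably, add a few perceived-safety or distress items and willingness items to the existing 1- and 5-month intervention-arm surveys. Report them as supportive proportions with responder numbers and exact two-sided 95% confidence intervals, and keep the interviews as planned. Otherwise, limit the timing sentence to usability and acceptability.
5. **If items are added**, treat them as aggregate survey outcomes. Section 10.1.3 says survey data are not linked to identity, while 8.3.4 requires each adverse event to be characterised and followed. These sections must be reconciled on how untraceable reports of distress are handled.

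The cost is slightly longer surveys, one table, wording changes, IRB approval before use (Statement of Compliance) and a more modest claim. No extra interviews are needed. Students who answer neither follow-up survey are still missed.

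A separate point to reconcile: section 5.5 selects interviewees by MKit user status, while 10.1.3 says email addresses will not be linked to app-use data.
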